7.2 Exclusion Criteria

The subject must be excluded from participating in the trial if the subject:

- 1. Has a history of clinically significant endocrine, gastrointestinal (including motility disorder and intestinal obstruction), cardiovascular, hematological, hepatic, immunological, renal, respiratory, genitourinary, or major neurological (including stroke and chronic seizures) abnormalities or diseases.
- 2. Has participated in another investigational trial within 4 weeks before the pretrial (Screening) visit. The 4-week window will be derived from the date of the last trial procedure and/or AE related to the trial procedure in the previous trial to the pretrial/Screening Visit of the current trial.
- 3. Is an employee or immediate family member (eg, spouse, parent, child, sibling) of the sponsor.
- 4. Has a history of cancer (malignancy).
- 5. Has a history of significant multiple and/or severe allergies (eg, food, drug, latex allergy) or has had an anaphylactic reaction or significant intolerance to prescription or nonprescription drugs or food.
- 6. Has a positive alcohol or drug screen.
- 7. Is a lactating/nursing woman.
- 8. Had major surgery, donated or lost 1 unit of blood (approximately 500 mL) within 8 weeks of the first dose of trial drug.
- 9. Has a known hypersensitivity to any component of the formulation of TAK-954 or related compounds, or to itraconazole (see Product Insert).
- 10. Is unable to refrain from or anticipates the use of any medication, including prescription and nonprescription drugs or herbal remedies, beginning approximately 7 days before administration of the initial dose of trial drug, throughout the trial (including washout intervals between trial periods), until the Follow-up Visit. There may be certain medications that are permitted, see Section [7.3](#).
- 11. Has a history of alcohol consumption exceeding 2 standard drinks per day on average (1 glass is approximately equivalent to: beer [354 mL/12 ounces], wine [118 mL/4 ounces], or distilled spirits [29.5 mL/1 ounce] per day).
- 12. Consumes excessive amounts, defined as greater than 6 servings (1 serving is approximately equivalent to 120 mg of caffeine) of coffee, tea, cola, energy drinks, or other caffeinated beverages per day.
- 13. Has a substance abuse disorder.

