6.2 Rationale for Trial Design, Dose, and Endpoints

6.2.1 Rationale of Trial Design and Dose

TAK-954 is a small molecule, 5-HT4 agonist. TAK-954 has been investigated in healthy subjects at single oral doses from 0.1 to 20 mg, multiple oral doses from 0.2 to 10 mg once daily (QD) for 10 days, and multiple IV doses from 0.1 to 0.5 mg QD for 5 days. A single IV dose of 0.5 mg TAK-954 has also been investigated in critically ill patients with enteral feeding intolerance and compared with metoclopramide. After multiple IV infusion dosing in healthy subjects (0.1 and 0.5 mg with a 1-hour infusion), TAK-954 concentrations declined in a biphasic manner, with mean $t_{1/2}$ values ranging from 18.0 to 18.9 hours on Day 5. TAK-954 steady state was achieved by Day 3 with minimal accumulation of TAK-954 after multiple IV dosing of 0.5 mg. The increase in exposure from the 0.1 mg to 0.5 mg IV dose was approximately dose proportional, and the mean amount of TAK-954 excreted unchanged in urine on Day 5 ranged from 27.7% to 31.6%. In subjects who were critically ill and received 0.5 mg by IV infusion, the PK exposure was slightly lower relative to that observed in healthy subjects.

Two active metabolites were identified nonclinically, but TAK-954 was not extensively metabolized to either of these metabolites after oral dosing (mean C_{max} and area under the concentration-time curve from time 0 to 48 hours metabolite to parent ratios ranged from 0.0008 to

0.004). Renal excretion of these metabolites was also low with concentrations in urine generally below the limit of detection. Evidence of GI prokinetic activity in healthy subjects (increased bowel movement frequency, looser stool consistency, and decreased time to first bowel movement) was observed at all dose levels after receiving single and multiple doses (oral and IV). In 7 subjects who were critically ill, scintigraphy data qualitatively suggest TAK-954 decreases gastric emptying time after a liquid meal.

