7.3 Excluded Medications, Supplements, and Dietary Products

Use of excluded agents (prescription or nonprescription) or dietary products is outlined in [Table 7.a.](#)

Table 7.a Excluded Medications, Supplements, and Dietary Products

Category	Between Screening and Enrollment (Days -28 to Predose [Day 1])	Randomization Post-Enrollment (Day 1) to Follow-up Visit
Tobacco- and nicotine-containing products	Completely restricted	Completely restricted
Cannabis products	Completely restricted	Completely restricted
Alcohol	Completely restricted 7 days before dosing	Completely restricted 7 days before dosing At all other times no more than 3 units/day
Xanthine and/or caffeine	Completely restricted 24 hours before dosing	Completely restricted 24 hours before dosing At all other times no more than 6 units/day
Medications	Completely restricted 7 days before dosing	Completely restricted (a)
Food substance		
Grapefruit /grapefruit juice	Completely restricted 7 days before dosing	Completely restricted
Fruit	No restriction	No restriction
Fruit juice	No restriction	Dosing will occur without consumption of fruit juice. Fruit juice is restricted 4 hours after dosing.
Mustard green (b)	Completely restricted 7 days before dosing	Completely restricted
Charbroiled meat	Completely restricted 7 days before dosing	Completely restricted

(a) If medications are required to treat an AE, certain medications may be allowed after discussion and agreement between the sponsor and principal investigator.

(b) Mustard green family includes kale, broccoli, watercress, collard greens, kohlrabi, Brussel sprouts, and mustard.

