7.6 Medication History and Concomitant Medications

Medication history information includes any medication relevant to eligibility criteria stopped at or within 28 days prior to signing of informed consent. Concomitant medication is any drug given in addition to the study drug, taken at any time from signing of informed consent through the end of study.

Medication history and concomitant medications will be coded using the WHODrug.

Listings for medication history and concomitant medications will be produced by site and subject number.

There will be no summary or inferential analysis of medication history and concomitant medications.

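### Minor: the 7-day window for all medicines does not look back further for CYP3A4 inducers or inhibitors, so a recent user can enter with a distorted Period 1 AUC

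*Protocol*

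**What the plan says.** Protocol 7.2, item 10, excludes a subject who "Is unable to refrain from or anticipates the use of any medication, including prescription and nonprescription drugs or herbal remedies", with the period "beginning approximately 7 days before administration of the initial dose of trial drug" and running to the Follow-up Visit. Table 7.a (Protocol 7.3) gives the Medications row "Completely restricted 7 days before dosing" up to enrolment. Its footnote only loosens the rule afterwards: "If medications are required to treat an AE, certain medications may be allowed after discussion and agreement between the sponsor and principal investigator".

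No criterion or table row names CYP3A4 inducers or inhibitors. The longer restrictions concern other things:
- item 2, "Has participated in another investigational trial within 4 weeks before the pretrial (Screening) visit";
- 6 months without nicotine (Protocol 7.1);
- no cannabis from Day -28 (Table 7.a).

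SAP 7.6 defines medication history as "any medication relevant to eligibility criteria stopped at or within 28 days prior to signing of informed consent", but it is only listed. Case-by-case exclusion from the PK analysis (Protocol 11.1.1, SAP 7.2) is for dosing noncompliance or incomplete data.

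The sequence is fixed. TAK-954 alone is given on Period 1 Day 1. Period 2 Day 1 follows at least 7 days later, and TAK-954 is repeated on Period 2 Day 4 during itraconazole, so the two TAK-954 doses are at least 7 + 3 = 10 days apart (Protocol 6.1 and 9.4).

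**The concern.** Item 10 looks forward from about Day -7. Someone who stopped an inducer or inhibitor on Day -8 meets it, and nothing later in the plan identifies that subject as a problem. If part of the effect remains on Day 1, it acts mainly on the reference period. By the second dose it has faded for at least 10 more days, and itraconazole is then inhibiting the same enzyme. With one sequence there is no second order to balance this, and within-subject pairing does not cancel an effect that sits in one period.

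Residual induction lowers the reference AUC and overstates the interaction. Residual inhibition raises it and understates the interaction. At stake is the AUC∞ ratio, one of two primary comparisons, from about 10 subjects.

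**Working it through.** **The plan's own figure.** The documents give no calculation behind the 7 days. The sample size can be reproduced. The stated distance is ln(1.5/1.25) = 0.182. The probability that the 95% half-width t(0.975, n-1)·s/√n is at most 0.182, with SD 0.187 (Cmax), is 88.4% at n = 9 and 94.7% at n = 10. So 10 is the smallest n reaching 90%. With SD 0.129 (AUC) it exceeds 99.9%. Cmax therefore sets N.

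**Inputs.**
- From the documents: about 10 completers; AUC SD of log differences 0.129; half-life 18.0 to 18.9 h; 27.7% to 31.6% of TAK-954 excreted unchanged (Protocol 6.2.1). The last caps the CYP3A4 share f at 1 - 0.316 to 1 - 0.277, about 0.7.
- Assumed, because the documents do not give them: f from 0.2 to 0.7; CYP3A4 clearance doubled at stopping; offset half-life t of 1.5, 3 or 6 days; a 7-day gap, about the shortest allowed; one affected subject in 10; no effect left at the second dose.

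**Formulas.** Residual r = 2^(-7/t). Period 1 clearance factor m = 1 + f·r, which also multiplies that subject's AUC ratio. Shift in the geometric mean ratio = m^(1/10) - 1.

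| f | t = 1.5 d, r = 0.039 | t = 3 d, r = 0.198 | t = 6 d, r = 0.445 |
|---|---|---|---|
| 0.2 | m 1.008; 0.1% | m 1.040; 0.4% | m 1.089; 0.9% |
| 0.4 | m 1.016; 0.2% | m 1.079; 0.8% | m 1.178; 1.7% |
| 0.7 | m 1.028; 0.3% | m 1.139; 1.3% | m 1.312; 2.8% |

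These hold r constant over the 120 h of sampling. Letting it decay lowers the bottom row to 0.2%, 1.1% and 2.5%.

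**Spread, worst cell.** One outlying log difference of ln 1.312 = 0.2715 among 10 adds 0.2715²/10 to the variance: √(0.129² + 0.1 × 0.2715²) = 0.155, an interval 0.155/0.129 = 1.20 times as wide.

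**Against planned precision.** The 90% half-width is 1.833 × 0.129/√10 = 0.075 on the log scale, or +7.8%/-7.2%. At SD 0.155 the half-width probability for AUC is still 99.6%.

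**Inhibition.** Assuming 90% inhibition at stopping, Period 1 AUC is multiplied by 1/(1 - 0.9·f·r). At f = 0.7 and t = 4 days (r = 0.297) this is 1.23, and the ratio falls by a factor 0.813^(1/10) = 0.98. At t = 6 days the factor is 0.719^(1/10) = 0.97.

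**Cmax.** In a one-compartment model (an assumption; the documented decline is biphasic), the level at the end of a 1-hour infusion is proportional to (1 - e^(-k))/k. With k = ln 2/18.5 = 0.0375 per hour, raising k by 31% lowers it by 0.6% in that subject, about 0.06% in the mean ratio.

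**Longer window.** At 28 days and t = 6, r = 0.039 and m = 1.03 at f = 0.7. At 14 days and t = 3, r is also 0.039.

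**The case against.** The strongest reply is that the effect is small and the scenario unlikely. Every cell of the table lies well inside the planned interval. Clinically significant disease, including chronic seizures, is excluded. The urine drug screen includes barbiturates and is done at Screening and at each admission. Medication use is reviewed, and a pre-lock review considers subject evaluability (Protocol 11.1). The documents also hint at limited metabolism: TAK-954 was relatively stable in hepatocytes, and two active metabolites were 0.0008 to 0.004 of parent after oral dosing. All of this stands and keeps the point minor. None of it closes the gap, because no rule covers a subject who complied with the 7 days.

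A reader might infer that both primary endpoints are at risk. The Cmax check does not support that.

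A reader might also infer a material bias. With 3- to 5-fold induction, offset half-lives of 1 to 4 days and f up to 0.7, one subject in 10 gives at most 1.06 and three in 10 at most 1.20. The documents offer no basis for three recently induced volunteers among 10.

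Nor do they establish 28 days as the required window. The SAP's 28 days runs back from consent and governs what is recorded, and item 2 concerns investigational trials. With a 3-day offset, 14 days would do as much as 28 does with a 6-day offset.

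**Conclusion.** The gap is real, but it is a minor weakness affecting AUC only. A recent user of a CYP3A4 inducer or inhibitor is eligible, and the fixed sequence puts any residual effect on the reference period. On the stated assumptions one induced subject in 10 shifts the AUC ratio by about 0.1% to 2.8%. In the worst case that subject's own ratio is inflated by 31% and the SD rises from 0.129 to about 0.155. With fast recovery the effect is negligible.

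The choice of N = 10 rests on Cmax and is untouched, and the AUC probability stays above 99% on the reading that reproduces N. The size depends wholly on recovery time, CYP3A4 share and prevalence of use, none of which the documents give.

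**What to change.** Keep the 7-day rule for medicines in general. Add to exclusion 10, and as a row in Table 7.a, a look-back criterion: no use of known CYP3A4 inducers or inhibitors, including herbal products, within 28 days before the first dose of trial drug, or within another window that the sponsor justifies from recovery of enzyme activity. Word it as an entry criterion only, so that it cannot be read as an instruction to stop any prescribed treatment. Check that the medication history collected reaches back far enough, since the SAP counts its 28 days from consent.

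Cost: one sentence and one table row, with no new visit or test. A few volunteers would be deferred or screened out.

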7.3 Excluded Medications, Supplements, and Dietary Products

Use of excluded agents (prescription or nonprescription) or dietary products is outlined in [Table 7.a.](#)

Table 7.a Excluded Medications, Supplements, and Dietary Products

Category	Between Screening and Enrollment (Days -28 to Predose [Day 1])	Randomization Post-Enrollment (Day 1) to Follow-up Visit
Tobacco- and nicotine-containing products	Completely restricted	Completely restricted
Cannabis products	Completely restricted	Completely restricted
Alcohol	Completely restricted 7 days before dosing	Completely restricted 7 days before dosing At all other times no more than 3 units/day
Xanthine and/or caffeine	Completely restricted 24 hours before dosing	Completely restricted 24 hours before dosing At all other times no more than 6 units/day
Medications	Completely restricted 7 days before dosing	Completely restricted (a)
Food substance		
Grapefruit /grapefruit juice	Completely restricted 7 days before dosing	Completely restricted
Fruit	No restriction	No restriction
Fruit juice	No restriction	Dosing will occur without consumption of fruit juice. Fruit juice is restricted 4 hours after dosing.
Mustard green (b)	Completely restricted 7 days before dosing	Completely restricted
Charbroiled meat	Completely restricted 7 days before dosing	Completely restricted

(a) If medications are required to treat an AE, certain medications may be allowed after discussion and agreement between the sponsor and principal investigator.

(b) Mustard green family includes kale, broccoli, watercress, collard greens, kohlrabi, Brussel sprouts, and mustard.

7.4 Diet, Fluid, and Activity

7.4.1 Diet and Fluid

Subjects must abstain from all food and drink (except water) at least 8 hours before any safety laboratory evaluations.

Water is permitted until 1 hour before TAK-954 and itraconazole administration. Water may be consumed without restrictions beginning 1 hour after TAK-954 and itraconazole dosing.

Subjects will receive a standard (moderate-fat) breakfast 1.5 hours before TAK-954 dosing in Trial Period 1 and 30 minutes before itraconazole dosing in Trial Period 2. Lunch will be provided approximately 4 hours after TAK-954 dosing or 5.5 hours after itraconazole dosing, as applicable, on all days. Dinner will be provided approximately 9 or 10 hours after TAK-954 or itraconazole dosing, respectively, on all days. An evening snack will also be permitted. The caloric content and composition of meals will be the same in each trial period. After the 24-hour postdose (Day 1 of Trial Period 1 and Day 4 of Trial Period 2) procedures have been completed, subsequent meals and snacks will be unrestricted in caloric content, composition, and timing.

7.4.2 Activity

Subjects will avoid unaccustomed strenuous physical activity (eg, weight lifting, running, bicycling) from the Screening Visit until the Follow-up Visit.

7.5 Criteria for Discontinuation or Withdrawal of a Subject

1. The subject experiences an AE that requires early termination because continued participation imposes an unacceptable risk to the subject's health or the subject is unwilling to continue because of the AE.
2. Liver Function Test (LFT) Abnormalities

In multidose studies, trial drug should be discontinued immediately with appropriate clinical follow-up (including repeat laboratory tests, until a subject's laboratory profile has returned to normal/baseline status, see Section 10.2.9.4), if the following circumstances occur at any time during trial drug treatment:

- Alanine aminotransferase (ALT) or aspartate aminotransferase (AST) >8 times the upper limit of normal (ULN), or
- ALT or AST $>5\times$ ULN and persists for more than 2 weeks, or
- ALT or AST $>3\times$ ULN in conjunction with elevated total bilirubin $>2\times$ ULN or international normalized ratio >1.5 , or
- ALT or AST $>3\times$ ULN with appearance of fatigue, nausea, vomiting, right upper quadrant pain or tenderness, fever, rash, and/or eosinophilia ($>5\%$).

3. Significant protocol deviation. The discovery that the subject failed to meet protocol entry criteria or did not adhere to protocol requirements, and continued participation poses an unacceptable risk to the subject's health.
4. Lost to follow-up. The subject did not return to the clinic, and attempts to contact the subject were unsuccessful. Attempts to contact the subject must be documented in the subject's source documentation.
5. Voluntary withdrawal. The subject (or subject's legally acceptable representative) wishes to withdraw from the trial. The reason for withdrawal, if provided, should be recorded in the electronic case report form (eCRF).

Note: All attempts should be made to determine the underlying reason for the withdrawal and, where possible, the primary underlying reason should be recorded (ie, withdrawal because of an AE should not be recorded in the “voluntary withdrawal” category).

6. Trial termination. The sponsor, IRB, or regulatory agency terminates the trial.

7.6 Procedures for Discontinuation or Withdrawal of a Subject

The investigator may discontinue a subject’s trial participation at any time during the trial when the subject meets the trial termination criteria described in Section 7.5. In addition, a subject may discontinue his or her participation without giving a reason at any time during the trial. Should a subject’s participation be discontinued, the primary criterion for termination must be recorded by the investigator. In addition, efforts should be made to perform all procedures scheduled for the Early Termination Visit.

7.7 Subject Replacement

If a subject discontinues from the trial, a replacement subject may be enrolled, if deemed appropriate by the investigator and sponsor. The trial site should contact the sponsor for the replacement of subject’s treatment assignment and allocation number.

8.0 CLINICAL TRIAL MATERIAL MANAGEMENT

8.1 Clinical Trial Drug

Details regarding the composition and extemporaneous preparation of the active ingredient are found in the Pharmacy Manual, Compounding Instructions, and/or similar documents. Clinical trial drug will be packaged to support enrollment and replacement subjects as required. When a replacement subject is required, the sponsor needs to be contacted before dosing.

Itraconazole will be supplied by the trial site.

8.1.1 Clinical Trial Drug Labeling

Clinical trial drug packaging will be affixed with a clinical label in accordance with regulatory requirements.

8.1.2 Clinical Trial Drug Inventory and Storage

Clinical trial drug must be stored in a secure, limited-access location under the storage conditions specified on the label. Inventory (receipt and dispensing) of trial drug must be recorded by an authorized person at the trial site.

8.1.3 Clinical Trial Drug Blinding

This is an open-label trial; therefore, the sponsor, investigator, and subject will know the treatment administered.

8.1.4 Accountability and Destruction of Sponsor-Supplied Drugs

The investigator is responsible for keeping accurate records of the clinical trial drug received from the sponsor or designee, the amount dispensed to and returned by the subjects, and the amount remaining at the conclusion of the trial. For all trial sites, the local country sponsor personnel or designee will provide appropriate documentation that must be completed for clinical trial drug accountability, return, and destruction.

8.1.5 Ancillary Supplies

All ancillary supplies will be provided by either the site or Takeda, based upon availability. If provided by Takeda, unused ancillary supplies will be accounted for and disposed of as directed by Takeda or a Takeda designee.

9.0 TRIAL PROCEDURES

The following sections describe the trial procedures and data to be collected as indicated in the Schedule of Trial Procedures (Section 3.0). For each procedure, subjects are to be assessed by the same investigator or site personnel whenever possible. Please note that it may become necessary to perform the following procedures at unscheduled time periods, per the discretion of the investigator. For information regarding procedures that are scheduled concurrently, see Section 6.3.4.

9.1 Administrative Procedures

9.1.1 Informed Consent Procedure

Informed consent must be obtained before the subject entering into the trial and before any protocol-directed procedures are performed. The requirements of informed consent are described in Section 13.2.

In the case where subjects have screening assessments performed prior to the trial, the data from the general/site screening could be included/used in the trial for those who were enrolled, as long as the procedure was performed within the protocol screening/enrollment window. A generic site screening form may be used.

9.1.2 Assignment of Screening Numbers

All consented subjects will be given a unique screening number that will be used to identify the subject for all procedures that occur before allocation. Each subject will be assigned only 1 screening number. Screening numbers must not be re-used for different subjects. Any subject who is screened multiple times will be assigned a new screening number for each screening event.

9.1.3 Inclusion and Exclusion Criteria

Each subject is assessed according to the eligibility criteria provided in Section 7.0.

9.1.4 Medical History/Demographics

Qualified site personnel are to collect subject significant medical history (past and ongoing) per the site's standard of care and appropriate clinical judgment as well as subject demographics.

